#### **9.1.1.3 Relationship of Adverse Events**

Assessment of causality of AEs to the study drug (IMM-101)

##### **Not related:**

An AE for which there is no reasonable temporal association between its onset and administration of the study drug, or that can reasonably be explained by other factors, including underlying disease, complications, concomitant drugs or concurrent treatment.

**Note:** Even if the Investigator feels there was no relationship to the study drug, the AE is to be reported.

**Unlikely to be related:** A clinical event, including laboratory test abnormality, with a temporal relationship to study drug administration which makes a causal relationship improbable, and in which other drugs, chemicals or underlying disease provide plausible explanations.

**Possibly related:** An AE for which there is a reasonable temporal association between its onset and administration of the study drug (including the course of treatment after withdrawal of the study drug) for which other causal factors may not be excluded.

**Probably related:** An AE for which there is a reasonable temporal association between its onset and administration of the study drug, including the course after withdrawal of the study drug, and which is more likely to be explained by the study drug than by any other cause (e.g. underlying disease, complications, concomitant drugs or concurrent treatment).

**Definitely related:** An AE that is judged as undeniably related to administration of the study drug. Factors taken into consideration when a definite relationship is assigned include whether the AE:

- Followed a clear temporal sequence from administration of the study drug.
- Could not be possibly explained by the known characteristics of the patient's clinical state, environmental or toxic factors, or other modes of therapy administered to the patient.
- Disappeared or decreased on cessation or reduction in dose of the study drug.
- Reappeared or worsened when the study drug was re-administered.
- Followed a response pattern known to be associated with administration of the study drug.

#### ***9.1.1.4 Intensity of Adverse Events***

All AEs (or toxicities) including local injection site reactions encountered during the study will be evaluated according to the NCI CTCAE v4.0 [5] grading system (0 to 5), where applicable.

Grade	Description
1	Mild; asymptomatic or mild symptoms; clinical or diagnostic observations only; intervention not indicated.
2	Moderate; minimal, local or non-invasive intervention indicated; limiting age-appropriate instrumental activities of daily living.
3	Severe or medically significant but not immediately life-threatening; hospitalisation or prolongation of hospitalisation indicated; disabling limiting self care activities of daily living.

CONFIDENTIAL

Immudulon Therapeutics Ltd.  
[name]

- 4 Life-threatening consequences; urgent intervention indicated.
- 5 Death related to AE.

#### **9.1.1.5 Treatment-Emergent Adverse Events**

All patients will have received IMM-101 in the context of both the Phase 1 study and on a Named Patient basis; therefore all AEs in this long term follow up study will be regarded as treatment-emergent.

#### **9.1.1.6 Unexpected Adverse Event / Adverse Drug Reaction**

An unexpected AE/ADR is an AE/ADR for which the nature or severity is not consistent with the applicable product information (e.g., IB for an unapproved investigational product or summary of product characteristics [SmPC] for an authorised product).

The term “expected” in pharmacovigilance is used to describe an event which might be anticipated from knowledge of the pharmacological properties of a substance. An event is also not to be described as “expected”, merely because it was foreseeable due to the health status (e.g., age, medical history) of the study patient. It refers strictly to the event being mentioned or listed in the applicable product information.

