The proposed dose of IMM-101 is 1 mg/dose (0.1 mL of a 10 mg/mL solution) administered intradermally. Previous experience in the Phase I safety and tolerability study in patients with melanoma has suggested that this dose is safe and well tolerated. The skin reaction that develops at the site of injection is characterized by erythema, local swelling and occasionally mild ulceration. All symptoms are to be expected given the known pharmacology of the product and previous extensive clinical experience with the closely related organism *M. vaccae*. Furthermore data from this safety and tolerability study with IMM-101 has

revealed that skin reactions resolve satisfactorily over time and appear not to be exacerbated by either prior or subsequent administration of IMM-101.

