#### **9.1.1.8 Suspected Unexpected Serious Adverse Reaction**

A suspected, unexpected serious adverse reaction (**SUSAR**) is defined as a suspected adverse reaction related to the study drug which occurs during the study, and that is both unexpected (i.e., not previously identified in nature, severity, or degree of incidence based upon the current Investigator’s Brochure [1]) and serious.

The term “expected” in pharmacovigilance is not used to describe an event which might be anticipated from knowledge of the pharmacological properties of a substance. An event is also not to be described as “expected”, merely because it was foreseeable due to the health status (e.g., age, medical history) of the study patient. It refers strictly to the event being mentioned or listed in the Investigator’s Brochure (1).

All SAEs, whether or not deemed drug-related or expected, must be reported to the relevant pharmacovigilance contact within 24 hours of knowledge by fax in the format detailed by the SAE Reporting Form (see Section 0).

**Note:** Hospitalisation/death due to disease progression will not be captured as an SAE if the disease progression/death is, in the Investigator's opinion, expected as normal course of the disease. However if the disease progression was faster than expected then a SAE will be reported.

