The IEC must be informed if the serious or unexpected adverse reaction, in the opinion of the Sponsor or the Investigator, is likely to affect the safety of the patients or the conduct of the study.

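### Does the reversed definition of an expected event in Protocol 9.1.1.6 change any safety classification or analysis?

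*Protocol*

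**What the plan says.** Protocol 9.1.1.6 has four sentences.

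1. It defines the term against a document: "An unexpected AE/ADR is an AE/ADR for which the nature or severity is not consistent with the applicable product information". The Investigator's Brochure is the example given for an unapproved product.
2. It then says that *expected* "in pharmacovigilance is used to describe an event which might be anticipated from knowledge of the pharmacological properties of a substance".
3. It adds that an event is *also not* expected merely because the patient's health made it foreseeable.
4. It closes: "It refers strictly to the event being mentioned or listed in the applicable product information".

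Section 9.1.1.8, on SUSARs, repeats sentences 2 to 4. There the term "in pharmacovigilance is not used to describe an event which might be anticipated from knowledge of the pharmacological properties of a substance", and the closing reference is to the Investigator's Brochure. That section has its own definition of unexpected: "not previously identified in nature, severity, or degree of incidence based upon the current" Investigator's Brochure. It also sets the reporting rule: "All SAEs, whether or not deemed drug-related or expected, must be reported to the relevant pharmacovigilance contact within 24 hours".

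Outside these two sections, two duties to the ethics committee use the word *unexpected*. One is in 9.4: "The IEC must be informed if the serious or unexpected adverse reaction, in the opinion of the Sponsor or the Investigator", is likely to bear on patient safety or study conduct. The other is in 13.2, which asks the investigator to tell the committee of unexpected serious adverse events under the same likely-effect condition.

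**The concern.** Section 9.1.1.6 is the protocol's general definition of an unexpected event, and one of its sentences says the opposite of what 9.1.1.8 says. Consider a reaction that could be foreseen from how the product works but is not listed in the Investigator's Brochure. Sentence 2 makes it expected; sentences 1 and 4, and 9.1.1.8, make it unexpected.

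Expectedness normally decides whether a serious reaction is reported onward as a SUSAR. A definition that lets pharmacology stand in for the listing could therefore suppress reports in a study whose main purpose is long-term safety. Section 7.3 seems to invite that reading, since it says of the injection-site reaction: "All symptoms are to be expected given the known pharmacology of the product".

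**Working it through.** No arithmetic applies to the definition itself. The check compares the two paragraphs, then follows the disputed label to every place where it could matter.

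**Comparing the paragraphs.** The *expected* paragraphs of 9.1.1.6 and 9.1.1.8 differ in two places: the missing *not*, and the closing reference (product information in one, Investigator's Brochure in the other). In 9.1.1.6 the *also not* of sentence 3 presupposes a negative in sentence 2, which 9.1.1.8 has and 9.1.1.6 lacks. Sentence 3 concerns health status, a different ground, so it does not itself conflict with sentence 2. Of four sentences, one is wrong and two (the first and last) contradict it. Restoring one word removes every conflict.

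**Following the label.** Take the reaction described above, foreseeable but unlisted.

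| Where the label could act | Does sentence 2 of 9.1.1.6 change the result? |
|---|---|
| SUSAR classification (9.1.1.8) | No. The section has its own test against the Investigator's Brochure and its own correct sentence. |
| 24-hour reporting of serious events (9.1.1.8, 9.4) | No. It applies whether or not the event is expected. |
| Ethics-committee notice (9.4), serious reaction | No. The condition is serious *or* unexpected, so seriousness is enough. |
| Ethics-committee notice (13.2), serious event | Formally yes, but a serious reaction is already caught by 9.4. |
| Ethics-committee notice (9.4), non-serious reaction | Yes, if it is also thought likely to affect patient safety or study conduct. |
| SAP Tables 10a to 10h | No. 0 of 8 use expectedness. |
| SAP Listing 12 | No. 0 of 13 columns hold expectedness. |

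On the 13.2 row, Protocol 9.1.1.2 counts an event as a reaction whenever a relationship to the product cannot be ruled out. An event foreseeable from the product's pharmacology will seldom fall outside that, so the overlap with 9.4 is close to complete.

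On the non-serious row, 13.2 separately requires written reports to the committee, at least annually, on any change that significantly affects conduct or raises risk to patients. That duty has no expectedness condition. It covers much of the same ground, though possibly later. Protocol 10.1.2 adds periodic presentation of data for the annual safety update report.

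**The 7.3 example.** Section 9.1.3.1 also describes local reactions as expected, and cites the Investigator's Brochure for the skin reaction and discomfort. On that citation the reaction is expected by the listing as well as by pharmacology. The disputed sentence is not shown to change its label.

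**Which text this is.** The supplied protocol logs seven amendments, and none mentions this wording. The SAP rests on version 9.0, which incorporates eight. So 8 − 7 = 1 amendment (8.0) has not been seen and may already have corrected the sentence.

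**The case for a change.** The best case for acting is that the error can be shown from the sponsor's own parallel text and costs one word to repair. Section 9.1.1.8 governs only SUSARs, so 9.1.1.6 is the definition that a reader of 9.4 or 13.2 would consult, and under 13.2 the label formally decides for serious events. A definition that contradicts itself should not be left to the reader's good sense when patient safety depends on it.

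The contradiction stands, and so does the low cost. The consequence does not follow. A reader who reaches sentence 2 meets *strictly* two sentences later and has just read a definition tied to the product information. Anyone classifying a SUSAR works from 9.1.1.8, where the sentence is right. The duty in 13.2 adds little once 9.4 has caught serious reactions. The documents show no event that was misclassified.

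Nor is it certain that the published protocol contains the slip. The text was read from a PDF by a program, and loss of one short word cannot be excluded, although the sentence is grammatically complete and shows no gap.

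A line in the study report declaring that expectedness was judged against the Investigator's Brochure would not help. Nothing in the documents shows how it was judged in practice, and no planned output uses it.

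**Conclusion.** This is a clerical slip, and no change to the plan follows. Sentence 2 of 9.1.1.6 contradicts its own section and 9.1.1.8 as supplied. The intended rule is still clear from the rest of the paragraph and is stated correctly where SUSARs are defined. SUSAR classification, 24-hour reporting of serious events, all eight adverse event tables and all 13 columns of Listing 12 are unaffected.

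The only practical residue is the ethics-committee notice in 9.4 for a non-serious, unlisted but pharmacologically foreseeable reaction judged likely to affect safety or conduct. The periodic reporting in 13.2 largely covers that case. The note to SAP Listing 1 records that the trial was terminated in December 2018, so amending the definition would no longer guide any reporting under it.

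The conclusion assumes that the missing word is not an artefact of reading the PDF and that Amendment 8.0 left the sentence alone. If either assumption fails, there is no inconsistency at all.

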#### **9.1.1.7 Serious Adverse Events**

A serious adverse event (SAE) is one that suggests a significant hazard, contraindication, side-effect, or precaution. With respect to human clinical experience, this includes any event that:

- Results in death (*other than due to disease progression*).
- Is life-threatening.\*
- Requires in-patient hospitalisation or prolongation of existing hospitalisation.
- Results in persistent or significant disability/incapacity.
- Is a congenital anomaly/birth defect.
- Other medically important condition.

\* Life-threatening in the definition of a SAE or adverse reaction refers to an event in which the patient *was at risk of death at the time of event*; it does not refer to an event, which hypothetically might have caused death if it were more severe.

All of the above criteria apply to the case as a whole and should not be confused with the outcomes of individual reactions/events. More than one of the above criteria can be applicable to the one event.

#### **9.1.1.8 Suspected Unexpected Serious Adverse Reaction**

A suspected, unexpected serious adverse reaction (**SUSAR**) is defined as a suspected adverse reaction related to the study drug which occurs during the study, and that is both unexpected (i.e., not previously identified in nature, severity, or degree of incidence based upon the current Investigator’s Brochure [1]) and serious.

The term “expected” in pharmacovigilance is not used to describe an event which might be anticipated from knowledge of the pharmacological properties of a substance. An event is also not to be described as “expected”, merely because it was foreseeable due to the health status (e.g., age, medical history) of the study patient. It refers strictly to the event being mentioned or listed in the Investigator’s Brochure (1).

All SAEs, whether or not deemed drug-related or expected, must be reported to the relevant pharmacovigilance contact within 24 hours of knowledge by fax in the format detailed by the SAE Reporting Form (see Section 0).

**Note:** Hospitalisation/death due to disease progression will not be captured as an SAE if the disease progression/death is, in the Investigator's opinion, expected as normal course of the disease. However if the disease progression was faster than expected then a SAE will be reported.

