Eighteen patients (95%) reported at least one treatment-emergent AE after receiving IMM-101. Over the course of the study, a total of 119 treatment-emergent AEs were reported. There were 86 reports of treatment-emergent AEs that would be accepted as typical of a post-vaccination state (such as injection site reactions, joint pains/aches, headaches and flu-like symptoms) occurring at all dose levels. These were mainly mild in intensity, mostly resolved in a matter of days and responded well to simple supportive medication (e.g. paracetamol). They were entirely consistent with the pooled information available on *M. vaccae*, a closely related organism, and were generally less intense than symptoms typically observed following Bacille Calmette-Guérin (BCG) vaccination of tuberculin negative individuals.

Sixteen patients (84%) reported at least one treatment-related AE. A total of 56 treatment-related events were reported; the most frequently reported treatment-related adverse events were in the ‘administration site conditions’ category. All these injection reactions (local swelling, pain, erythema and occasionally mild ulceration) were considered ‘non-serious’ by the Investigator; no patient withdrew due to an intolerable injection site reaction.

Only one serious adverse event (SAE) was reported; one patient in the IMM-101 0.5 mg group was hospitalised with progressive shortness of breath and found to have progressive disease (metastatic lung lesion). The SAE was reported to be unrelated to IMM-101 by the Investigator.

The data collected at site to document and characterise injection site reactions indicated a trend for resolution over time, with the earlier and older skin reactions appearing reduced in size compared to the more recent ones at the end of the study. Furthermore, it appears that repeated administration does not predispose the patient towards larger or more intense reactions after subsequent administrations.

In summary, the study was conducted per protocol and provided considerable knowledge concerning the administration of IMM-101 and management of any side-effects. The AEs observed so far with IMM-101 are in line with expectations, are manageable and are in keeping with data from non-clinical models and past experience in humans with similar whole cell mycobacterial preparations. The injection site reactions are consistent for this

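### The SAE definition and the later Note on disease progression classify two of four kinds of progression event differently, and an unanchored Investigator opinion decides the Note.

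*Protocol*

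**What the plan says.** Protocol Section 9.1.1.7 lists six criteria, any of which makes an event serious. The death criterion carries an exception, "other than due to disease progression", with no condition on how fast the disease progressed. The hospitalisation criterion reads "Requires in-patient hospitalisation or prolongation of existing hospitalisation" and has no exception for progression.

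The Note at the end of Section 9.1.1.8, under the SUSAR heading, applies a different rule to both outcomes. It says "Hospitalisation/death due to disease progression will not be captured as an SAE" on condition that the event is "in the Investigator's opinion, expected as normal course of the disease". It then adds that "if the disease progression was faster than expected then a SAE will be reported". Section 9.1.1.8 also requires every SAE to be reported within 24 hours.

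Neither section says how the Investigator should decide what course is expected. Section 8.2 leaves tumour evaluation to standard care, with no protocol-specified method.

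The SAP (Section 9.3) summarises serious events in Table 10e and in the SAE rows of Table 10a, and non-serious events in Table 10g. It has no rule for progression events.

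**The concern.** A site that follows the definition and a site that follows the Note can classify the same event differently, and both would be complying with the protocol. Safety is the primary objective (Protocol Section 9.1) and SAEs are one of its named summaries (Section 10.1.1.1), so the seriousness flag should have one meaning throughout.

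The Note also rests on a judgement with nothing to anchor it. The study is open-label and uncontrolled, and there is no scan schedule, reference rate of progression or adjudication. The wording adds to the difficulty. Earlier in Section 9.1.1.8, an event may not be called expected merely because the patient's state of health made it foreseeable; the Note then uses the word in roughly that sense.

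The kind of event is not hypothetical. The only SAE in the Phase I study was a patient "hospitalised with progressive shortness of breath and found to have progressive disease" (Protocol Section 3.3). Under Section 9.1.1.7 such an admission counts. Under the Note it counts or not according to the Investigator's view of the pace.

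**Working it through.** The plan has no figure to reproduce: Protocol Sections 10.2 and 10.3 give sample size and significance level as not applicable. The check is a comparison of the two rules, followed by simple arithmetic for scale.

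**Step 1: the two rules side by side.** Event type is crossed with pace, and each 9.1.1.7 criterion is taken on its own.

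| Event due to progression | Section 9.1.1.7 | Note in 9.1.1.8 | Agree? |
|---|---|---|---|
| Death, expected course | Not an SAE (death criterion) | Not an SAE | Yes |
| Death, faster than expected | Not an SAE (death criterion) | SAE | **No** |
| Hospitalisation, expected course | SAE | Not an SAE | **No** |
| Hospitalisation, faster than expected | SAE | SAE | Yes |

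The rules conflict in 2 of 4 cells, one for each event type. The conflicts run in opposite directions: moving from the definition to the Note adds faster-progression deaths and removes expected-course hospitalisations.

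**Step 2: which outputs depend on the flag.**

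- Dependent: 24-hour reporting; the SAE rows of Table 10a, including the related-SAE rows; Table 10e; Table 10g, which receives an event recorded as an AE but not flagged serious.
- Not dependent: Table 10f, which takes adverse events leading to withdrawal or death without a seriousness condition; Table 1, which has its own row for death due to progression; overall survival, which counts death from any cause (Protocol Section 8.1).

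**Step 3: scale.** The size of the Safety Population is not stated. Protocol Section 4.2 gives 18 eligible Phase I patients, of whom 3 had died, 1 had stopped for pregnancy and 2 had stopped for unknown reasons by August 2011: 18 − 3 − 1 − 2 = 12 possible entrants. This is an indication only, so a range of 8 to 18 is used. One reclassified patient, with no other SAE, changes SAE incidence by 1/N:

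- N = 8: 1/8 = 12.5 points
- N = 10: 1/10 = 10.0 points
- N = 12: 1/12 = 8.3 points
- N = 18: 1/18 = 5.6 points

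At N = 12, the exact (Clopper-Pearson) 95% interval is 0 to 26.5% for 0/12 and 0.2 to 38.5% for 1/12.

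**The case against.** The strongest reply is that this is a drafting fault and not a true contradiction. Section 9.1.1.7 removes progression from one criterion of six, and says that the criteria apply to the case as a whole and that more than one can apply. A death from unexpectedly fast progression could still be serious as life-threatening, through hospitalisation, or as medically important. For hospitalisation, the Note can be read as a specific capture rule that qualifies a general definition.

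Both readings are fair, and they narrow the point without removing it. Whether another criterion rescues a given death depends on the case; it does not make the death criterion and the Note say the same thing. Reading the Note as an exception settles hospitalisation only if sites read it that way, and nothing tells them to.

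Four stronger readings are tempting, and the documents do not support them:

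- *The two sections give opposite answers on progression events.* They agree in two of the four cases.
- *SAE counts differ between the two sites, or from Phase I.* Nothing shows that the sites applied different rules, and the Phase I SAE definition is not in these documents. Counts could differ; that they do is not shown.
- *Progression events vanish from the safety report.* The Note removes SAE status, not the duty to record adverse events (Protocol Section 9.4). Progression deaths also appear in Table 1 and in overall survival, and Listing 17 gives the cause of deaths after withdrawal.
- *Most serious events here are affected.* That would rest on one Phase I event.

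It is also true that no inference is planned, that there is no comparison arm for opinion to bias differentially, and that a shift of 1/N applies to any binary item in so small a cohort.

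**Conclusion.** The point holds in a limited form. The protocol's SAE definition and its Note on progression conflict in two of four cases: death from faster-than-expected progression (where no other seriousness criterion applies) and hospitalisation for expected-course progression. The Note turns on Investigator opinion with no stated basis and no protocol-specified tumour assessments behind it.

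The effect is confined to the seriousness flag and what follows from it: 24-hour reporting, the SAE rows of Table 10a, and the split between Tables 10e and 10g. Table 10f, the death counts in Table 1 and overall survival are unaffected. Hospitalisations are the more exposed class, because those survival and disposition outputs capture deaths only.

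One reclassified patient is worth about 6 to 12.5 percentage points of SAE incidence, on the assumption that N lies between 8 and 18. That is small beside the sampling uncertainty, but visible in a descriptive table. The change should be made. It does not threaten the study's conclusions on survival.

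**What to change.** The sponsor should reconcile Section 9.1.1.7 with the Note in 9.1.1.8 so that they state one rule, and give the basis on which progression counts as expected. Which rule to adopt is for the sponsor; the need is that there be only one.

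The SAP's Listing 1 notes that the trial was terminated in December 2018, and the SAP took effect on 10 April 2019, so a new case report form field would come too late. The SAP, or the study report as a documented deviation, should instead:

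- state which rule was applied when events were classified;
- identify progression-related deaths and hospitalisations from data already held: the adverse event listing (Listing 12), disposition (Listing 1 and Table 1) and cause of death (Listing 17);
- show the SAE rows of Table 10a, and Table 10e, with and without those events, with the matching change in Table 10g.

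One limit should be declared. Listing 12 gives a reason for seriousness, so an admission never flagged as serious may be identifiable only from comments or source records.

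The cost is a small amount of extra review in a small cohort, a few added rows, and a few more serious events on display.
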